8.2.7. Patient Global Impression of Change (PGIC)

Patient Global Impression of Change (PGIC) will be collected at Week 4, Week 8, Week 12 and Week 16.

A 7-point scale is used, representing the degree to which the general state of health have changed relative to start of the study. On the PGIC, 1 = very much improved and 7 = very much worse.

A frequency table will summarize the responses for each treatment by visit. To take into account the ordinal nature of the response, p-values based on the Wilcoxon rank sum test comparing each rhNGF to Placebo will be computed.

PGIC data will be also listed.

This document is confidential.

8.2.8. EQ-5D-3L

EQ-5D-3L will be collected at screening, baseline, Week 4, Week 8, Week 12 and Week 16.

The Questionnaire EQ-5D-3L is a 5-dimension instrument assessing quality of life. The 5 dimensions are Mobility, Self-Care, Usual Activity, Pain/Discomfort, and Anxiety/Depression. Each dimension is scored as 1 = no problem, 2 = some problem, and 3 = extreme Problem.

No imputation will be done on missing values.

Descriptive summary statistics for the single dimension scores ("Mobility", "Self-Care", "Usual Activities", "Pain/Discomfort" and "Anxiety/Depression") will be presented by visit and treatment group.

Shift tables comparing results from Baseline to each visit will be presented with percentages based on subjects with a non-missing value at Baseline and post-baseline visit.

The patients provide an assessment of their best health state by means of a score between 0 and 100 (EQ visual analogue scale – VAS).

The change in VAS score from the baseline visit to the post-baseline visit will be analyzed using an mixed

model for repeated measures (MMRM). The analyses will include the fixed, categorical effects of treatment (3 levels: rhNGF 20 µg/ml TID, rhNGF 20 µg/ml BID and vehicle TID), visit (4 levels: Weeks 4, 8, 12, 16) and treatment by visit interaction. Subject will be considered as a random effect. The covariance matrix used will be "unstructured". Comparisons versus vehicle TID will be provided using least square means at each visit and overall.

EQ-5D-3L data will be listed.

8.3. Exploratory Endpoint

All exploratory endpoints will be summarized using Full Analysis Set. Statistical testing has only a descriptive value.

8.3.1. Proportion and frequency of preservative-free artificial tears use (n° drops/day) during the treatment period

The proportions and n° drops/day (see definition in 6.2.6) will be summarized during the treatment period, by treatment group.

8.3.2. Proportion and Frequency of Preservative-Free Artificial Tears Use (n° drops/day) During the Follow-Up Period

The proportions and n° drops/day (see definition in 6.2.6) will be summarized during the follow up period, by treatment group.

8.3.3. Change from Baseline in Schirmer Test I (Without Anesthesia) Versus Week 2

Change from baseline in Schirmer test I (without anesthesia) at Week 2 will be analyzed using the same analysis used for the primary efficacy end-point.

This document is confidential.

8.3.4. Change from Baseline in Symptoms Questionnaire (SANDE) Scores for Severity and Frequency Assessed at 2 Weeks

Change from baseline in symptoms questionnaire (SANDE) scores for severity and frequency assessed at 2 weeks will be analyzed using the same analysis used for the primary efficacy end-point.

8.3.5. Change from Baseline in Corneal and Conjunctiva Vital Staining with Fluorescein (NEI Scales) Versus Week 2

Change from baseline in corneal and conjunctiva vital staining with fluorescein (NEI scales) versus Week 2 will be analyzed using the same analysis used for the primary efficacy end-point.

8.3.6. Change from Baseline in Tear Film Break-Up Time (TFBUT) Versus Week 2

Change from baseline in TFBUT versus Week 2 will be analyzed using the same analysis used for the primary efficacy end-point.

8.3.7. Number of Patients who Experienced a Worsening in Symptom Scores (SANDE) and/or NEI Score \geq 50% Assessed at Week 2

Number of patients who experienced a worsening in symptom scores (SANDE) and/or NEI score \geq 50% assessed at Week 2 will be summarized by treatment group.

8.3.8. Change from Baseline in Goblet Cells Density at week 4

Goblet cells density is measured at baseline, Week 4 and Week 16.

Change from baseline in goblet cells density at Week 4 will be analyzed using the same analysis used for the primary efficacy end-point.

The goblet cells density will be summarized using descriptive statistics for continuous variables by treatment and visit. The change from baseline value will also be summarized for all post-baseline visits.

Goblet cells density will be also listed

8.4. Post Hoc Endpoint

Some correlation between sign and symptom scores could be computed for exploratory purpose.

This document is confidential.

9. Safety

The population used for safety analyses will be the Safety Set (SS). Safety will be assessed on the basis of adverse events (AEs).

Safety tables are presented in tables 14.1.5.1 and 14.1.5.2 and 14.3.1.1 to 14.3.2.4 ((see section15)

9.1. Extent of Exposure

The study drug administration (Day 1 to Week 4) will be captured in the patient diary including the administration of preservative-free artificial tears (Day 1 to Week 12).

The extent of exposure, otherwise referred to as the time from first instillation of study medication to last instillation of study medication is defined as:

Number of days on treatment = date of last instillation of treatment – date of first instillation of treatment +1

The data will be summarized by treatment group and presence/absence of primary Sjogren. A listing will be also provided.

9.2. Treatment Compliance

The assessment of patients' compliance to the IMP will be made by determining the number of drops administered to the eligible eye (see section 6.2.5).

Gross noncompliance will be defined as compliance for the eligible eye lower than 80% or greater than 120% and in case of gross noncompliance the patient will be excluded from the Per Protocol set.

9.3. Adverse Events / Adverse Drug Reactions

Adverse events (AEs) will be coded by SOC and PT, using the Medical Dictionary for Regulatory Activities (MedDRA 21.1).

Treatment-emergent adverse events (TEAEs) are all events occurring or worsening after the first dose of the IMP.

TEAEs will be summarized by SOC ,PT, treatment arm and phase (Treatment phase or Follow up). Both the number and percentage of patients who experience the event and the number of events will be summarised per treatment arm. Percentages will be based on the number of patients in the Safety Set.

All tables for TEAEs will be also summarized separately for each strata.

An overall summary of the number and percentage of patients and number of the events with any TEAEs, Potentially Related TEAEs, Serious TEAEs, Serious Potentially Related TEAEs, TEAEs leading to study discontinuation, TEAEs leading to death and TEAE of special interest (AESI) will be generated, and presented by treatment arm and phase (Treatment phase or Follow up)

TEAEs will be sorted alphabetically by SOC, and then sorted alphabetically by PTs within SOC.

Separate tables will be presented by severity, and for SAEs, ocular TEAEs, related ocular TEAEs, related TEAEs, and TEAEs leading to study discontinuation.

This document is confidential.

“Possible”, “probable”, “highly probable” or missing relationships are to be considered as related to study drug for the summary tables. “None” and “unlikely” relationships are to be considered not related to study drug.

Individual AEs will be listed in patient data listings. A listing of patients died due to COVID-19 will be also provided on randomized set.

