# 7.1.4. Safety endpoint

• Incidence and frequency of Treatment-emergent adverse events (TEAEs), assessed throughout the study.

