The study stopped to 261 patients instead of 300 originally planned; last subject enrolled was on March 25th, 2020. On March 9th, 2020 256 patients were randomized. Among them 185 had completed the study and 44 were early terminated subjects. So only 27 subjects are ongoing and 5 not randomized at the time of national emergency due to COVID-19.

Patients affected by COVID-19 will be identified using through Adverse form and Meddra coding (Preferred Term = 'Coronavirus infection').

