5.3. Safety Analysis Set

The Safety Analysis Set (SAF) will consist of all patients in the Randomized Set who took at least one dose of investigational product (IP) . This analysis set will be used for the safety analysis. Patients will be analyzed according to the treatment received.

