13.2.5.2. Table Conventions

- Units will be included where available.
- If the categories of a parameter are ordered, then all categories between the maximum and minimum category are presented in the table, even if $n = 0$ for all treatment groups in a given category that is between the minimum and maximum level for that parameter. For example, the frequency distribution for symptom severity would appear as:

| Severity Rating | N |
|-----------------|---|
| severe | 0 |
| moderate | 8 |
| Mild | 3 |

Where percentages are presented in these tables, zero percentages will not be presented and so counts of 0 will be presented as 0 and not as 0 (0%).

- If the categories are not ordered (e.g., Medical History), then only those categories for which there is at least 1 patient represented in 1 or more groups are included, except for reasons for discontinuations where all categories will be shown.
- Unknown or Missing categories are added to each parameter for which information is not available for 1 or more patients.
- Unless otherwise specified, the estimated mean and median for a set of values are printed out to 1 more significant digit than the original values, and standard deviations are printed out to 2 more significant digits than the original values. The minimum and maximum should report the same significant digits as the original values. For example, for systolic blood pressure:

| | |
|---------|-------|
| N | XX |
| Mean | XXX.X |
| Std Dev | X.XX |
| Median | XXX.X |
| Minimum | XXX |
| Maximum | XXX |

- P-values are reported in the format: "0.xxx", where xxx is the value rounded to 3 decimal places.
- Percentage values are printed to one decimal place, in parentheses with no spaces, one space after the count (e.g., 7 (12.8%), 13 (5.4%)). Unless otherwise noted, for all percentages, the number of patients in the analysis set for the treatment group who have an observation will be the denominator. Percentages after zero counts should not be displayed and percentages equating to 100% are presented as 100%, without decimal places.
- As general rule, the percentage of patients is calculated as a proportion of the number of patients assessed in the relevant treatment group (or overall) for the analysis set presented.
- Where a category with a subheading (such as system organ class) has to be split over more than one page, the subheading will be followed by "(cont)" at the top of each subsequent page.

This document is confidential.

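### Follow-up adverse event percentages use the whole Safety Set, so patients not observed after the treatment phase count as event-free and follow-up incidence is understated by their share

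*SAP*

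**What the plan says.** The only safety endpoint, in Protocol 7.1.4 and again in SAP 4.4, is "Incidence and frequency of Treatment-emergent adverse events (TEAEs), assessed throughout the study". SAP 9.3 adds a breakdown by phase in two places. For the main table: "TEAEs will be summarized by SOC ,PT, treatment arm and phase (Treatment phase or Follow up"). For the overall summary (any, related, serious, leading to discontinuation or death, special interest), results are "presented by treatment arm and phase (Treatment phase or Follow up"). It also asks for all TEAE tables to be repeated within each Sjögren stratum.

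The denominator is fixed once, with no distinction by phase: "Percentages will be based on the number of patients in the Safety Set". SAP 5.3 defines that set as "all patients in the Randomized Set who took at least one dose of investigational product (IP"); reaching follow-up is not a condition. The SAP defines no follow-up analysis set and plans no rate per unit of exposure. SAP 13.2.4 puts the analysis-set size in the column header, so a follow-up column would carry the full Safety Set N.

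On attrition, SAP 2 reports the position at 9 March 2020, when 256 patients had been randomized: "Among them 185 had completed the study and 44 were early terminated subjects".

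**The concern.** Follow-up lasts 12 weeks against 4 weeks of dosing, and Protocol 3.3 and 6.2 give safety as its purpose. A reader will take a follow-up percentage as the proportion of patients who had an event after treatment ended. With the stated denominator it is something else: patients with a recorded follow-up event, divided by everyone ever dosed. Anyone not observed in follow-up adds nothing to the numerator and one to the denominator.

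The direction of the error is known: downward. If the arms lose different shares of patients before follow-up, the arm with the greater loss has its percentage lowered more, and the comparison between arms shifts.

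**Working it through.** The plan states no follow-up percentage to reproduce. What can be checked is the attrition count and the effect of the denominator.

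**Inputs**
- Denominator: all Safety Set patients (SAP 9.3, 5.3).
- Status at 9 March 2020 (SAP 2): 256 randomized, 185 completed, 44 terminated early, 27 ongoing.
- Time and arm of the 44 terminations: not given.

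**Step 1. The counts reconcile.** 185 + 44 + 27 = 256.

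**Step 2. Effect of the denominator.** In one arm, let N be the Safety Set size, d the share with no observation after the treatment phase, and r the proportion with an event among those observed. Patients with a recorded event = r × N × (1 − d). Dividing by N gives

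reported % = r × (1 − d),

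so the relative understatement is d.

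**Step 3. Range for d.** The lower end is 0, if every early terminator left during follow-up or was still followed. The upper end for these patients is 44/256 = 17.2%, if none was observed after the treatment phase. This uses randomized patients as a stand-in for the Safety Set. Restricting to patients with a known final status would give 44/(185 + 44) = 44/229 = 19.2%.

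**Step 4. What that does to a percentage.** The values of r are assumed for illustration.

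| d | true 10% reported as | true 20% reported as |
|---|---|---|
| 0 | 10.0% | 20.0% |
| 5% | 9.5% | 19.0% |
| 10% | 9.0% | 18.0% |
| 15% | 8.5% | 17.0% |
| 17.2% | 8.3% | 16.6% |

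At the upper end the loss is 1.7 points on a true 10% and 3.4 points on a true 20%.

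**Step 5. Between arms.** With equal true risk, the apparent risk ratio is (1 − d₁)/(1 − d₂). Equal loss gives 1.00. An assumed 20% against 10% gives 0.80/0.90 = 0.89, so a true 20% in both arms is reported as 16% and 18%.

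**Step 6. By stratum.** The Sjögren stratum was planned at a minimum of 20 patients per arm (Protocol synopsis). At that size each unobserved patient is 1/20 = 5% of the denominator.

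**The case against.** Four arguments have force.

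- **Stopping early is not the same as being unobserved.** Protocol 6.3.1 asks for the follow-up assessments to be performed after discontinuation unless consent is withdrawn, and Protocol 8.4.1 asks for SAEs that come to light after participation ends. This stands, and it is why the lower end of the range is 0.
- **The SAP has a general rule that would avoid the problem.** SAP 13.2.5.2 says "the number of patients in the analysis set for the treatment group who have an observation will be the denominator". But that rule yields wherever something else is specified, and 9.3 does specify something else. If the general rule was meant, 9.3 still needs a sentence to say so.
- **Other outputs help.** Events that drive patients out are counted in the treatment phase and in the discontinuation tables, patient and event counts appear beside percentages, and discontinuation dates are listed (SAP 7.1). A careful reader could approximate the follow-up N from the listings. The disposition table will not supply it, because it is not split by phase.
- **The proposed denominator has a weakness of its own.** It conditions on something that happens after randomization, and it does not deal with patients who leave partway through follow-up. Both points stand and shape the fix.

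A reader might also infer more than the documents support. The phase split is stated for two kinds of summary only: the sentence in 9.3 on separate tables does not mention phase, nor do the titles in the SAP 15 index. The 17.2% is pooled and dated, so it is not a limit for any one arm or for the final data. Nothing in the documents shows that loss differs by arm, so a masked imbalance is a possibility and not a finding. The endpoint in Protocol 7.1.4 covers the whole study, for which a Safety Set denominator is conventional.

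**Conclusion.** The point holds for the follow-up columns of the SOC/PT and overall TEAE summaries, and for their repeats by stratum. Those percentages are understated by the share of Safety Set patients with no observation after the treatment phase. From the early terminations known at 9 March 2020, the pooled relative understatement lies between 0 and about 17%; the documents do not allow it to be narrowed. This assumes that the randomized count is close to the Safety Set, and it leaves out any later losses among the 27 patients then ongoing and those randomized afterwards. A single arm or stratum could lie outside the pooled range. Distortion between arms requires unequal loss, which is not documented.

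Treatment-phase tables, whole-study TEAE incidence and all efficacy analyses are unaffected, and the phase tables are descriptive. This is an inexpensive improvement to the follow-up tables and does not call the safety endpoint into question.

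**What to change.** In SAP 9.3:

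1. State that follow-up percentages use Safety Set patients with at least one visit or contact after the end of the treatment phase. Remote visits under SAP 2.1 should count.
2. Define where the treatment phase ends, for analysis purposes, in patients who stop dosing early, so that both their events and their membership of the denominator can be assigned.
3. Show this N by arm and stratum in the column header of the follow-up columns.
4. Keep the Safety Set denominator for treatment-phase and whole-study tables.
5. Optionally add events per person-time for follow-up, which also handles patients who leave partway through it.

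The cost is a sentence or two in the SAP and one extra count per arm and stratum in the table programs; no new data are needed for the count. Because the new denominator conditions on a post-randomization event, the follow-up columns should be read beside the whole-study Safety Set table.

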9.4. Laboratory Evaluations

Not applicable

9.5. Vital Signs

Not applicable

9.6. ECG

Not applicable

9.7. Physical Examination

Not applicable

This document is confidential.

10. Interim Analyses

No interim analysis was planned

This document is confidential.

11. Changes from Analysis Planned in Protocol

IDEEL and EQ-5D will be analysed using a mixed model for repeated measures (MMRM) instead of analysis of variance as the method seems more appropriate due to the repeated measures.

Exploratory sensitivity analysis will be also conducted for SANDE, Schirmer Test II, Corneal and Conjunctiva Vital Staining and TFBUT instead of only primary efficacy endpoint.

Overall compliance will not be calculated, as we don't have in the database the number of unused vials. We only have the number of vials not returned to the site whatever the reasons

Additional analyses have been planned to investigate the impact of COVID-19 pandemic on primary endpoint and on patient safety profiles (in case of 10% randomized patients affected).

Summary statistics on primary endpoint reporting the two treatment doses (20 µg/mL BID arm and 20 µg/mL TID) pooled versus placebo has been added to see the overall effect of the rhNGF treatment.

A sensitivity analysis on primary endpoint based on classification of patients in "Responders" and "Non Responders" based on the Schirmer Test I at the end of treatment has been added. This analysis will assess the robustness of results by considering an exact statistical method (not depending on assumption of normality of the data) and based on the status of the patients at the end of treatment.

This document is confidential.

12. Reference List

1. Williams DA. The comparison of several dose levels with a zero dose control. 1972. Biometrics 28, 519-531.
2. Williams DA. A test for differences between treatment means when several dose levels are compared with a zero dose control. 1971. Biometrics 27, 103-117.
3. Shein-Chung Chow, Jun Shao, Hansheng Wang; Samples Size Calculations in Clinical Research - Marcel Dekker, Inc. 2003I, SBN: 0-8247-0970-5, p. 186-189.
4. F Amparo, DA Schaumberg, R Dana; Comparison of two questionnaires for dry eye symptom assessment: the ocular surface disease index and the symptom assessment in dry eye Ophthalmology 2015 July; 122 (7), 1498 - 1503

This document is confidential.

13. Programming Considerations

All tables, figures, listings (TFLs), and statistical analyses will be generated using SAS for Windows, Release 9.4. (SAS Institute Inc., Cary, NC, USA). Computer-generated table, listing and figure output will adhere to the following specifications.

13.1. General Considerations

- One SAS program can create several outputs, or a separate SAS program will be created for each output.
- One output file can contain several outputs.
- Output files will be delivered in Rich Text Format (RTF) that can be manipulated in MSWord.
- Numbering of TFLs will follow ICH E3 guidance.

13.2. Table, Listing, and Figure Format

13.2.1. General

- All TFLs will be produced in landscape format on A4 paper size, unless otherwise specified.
- All TFLs will be produced using the Courier New font, size 8 which is the smallest acceptable point size for the Regulatory Authorities.
- The data displays for all TFLs will have a minimum blank 1-inch margin on all 4 sides.
- Headers and footers for figures will be in Courier New font, size 8 which is the smallest acceptable point size for the Regulatory Authorities.
- Legends will be used for all figures with more than 1 variable, group, or item displayed.
- TFLs will be in black and white (no color), unless otherwise specified.
- Specialized text styles, such as bolding, italics, borders, shading, and superscripted and subscripted text, will not be used in the TFLs, unless otherwise specified. On some occasions, superscripts 1, 2, or 3 may be used (see below).
- Only standard keyboard characters will be used in the TFLs. Special characters, such as non-printable control characters, printer-specific, or font-specific characters, will not be used. Hexadecimal-derived characters will be used, where possible, if they are appropriate to help display math symbols (e.g., μ). Certain subscripts and superscripts (e.g., cm², C_{max}) will be employed on a case-by-case basis.
- Mixed case will be used for all titles, footnotes, column headers, and programmer-supplied formats, as appropriate.

13.2.2. Headers

- All output should have the following header at the top left of each page:
- Dompé farmaceutici S.p.A

Protocol NGF0118

Draft/Final Run <*date*>

This document is confidential.

- All outputs should have Page n of N at bottom right corner of each page. TFLs are internally paginated in relation to the total length (i.e., the page number should appear sequentially as page n of N, where N is the total number of pages in the table).
- The date in which output was generated should appear along with the program name as a footer on each page.

